#### Secondary Outcome Variable Data.

The secondary outcome variables will be the number of subjects experiencing adverse events (both objective and subjective). This data will be provided by the subjects or observed, measured or verified by the investigators and will be documented on the adverse events section of the Ketorolac Research Form. Adverse events will be documented as objective and subjective adverse events. Subjects will be provided a list of the most common adverse events based on the medical website UpToDate.com. This list will be included on the Ketorolac Research Form. Subjects will be advised to circle any of the adverse events that they are experiencing. Each circled adverse event will count as 1 in a binary numbering system (1 indicating an adverse event and 0 indicating no adverse event) for purposes of analysis. Subjects may have more than one adverse event and each event will count as 1 point. The definitions of objective and subjective adverse event are provided below.

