Study participants whose randomized dosing regimens are rejected by the attending provider will be excluded from the study. Again, attending provider concurrence with the randomized ketorolac dosing utilized in this study will be documented on the Ketorolac Research Form and is reviewed in the inclusion and exclusion portion of this application.

Prior to administration of ketorolac, a review of systems (ROS) will be performed with each patient to ensure that the subject has no medical history or other acute medical problems which would meet exclusion criteria for this study. However, this information will not be documented on any forms and will not be accessed through the EHR. The ROS is an anatomic or physiologic systems based detailed

interview with the patient to discuss their overall health and to identify any other medical issues that may or may not be connected with the patient's reason for ED visit.

The ROS used for this study is located within this application and will be located in the appendix of the manuscript when this study is complete. The study investigators' ROS may be separate from the actual attending provider ROS. The attending provider will perform their own ROS based on standard medical history taking. However, the ROS performed by the investigators for the purpose of this study will be used to discover any other medical issue or issues which may meet inclusion or exclusion criteria. If deemed pertinent to patient care, information obtained by performing the investigator ROS will be communicated verbally to the attending provider, so that they are aware that the patient may require evaluation for medical issues beyond an acute MSK injury or pain.

Ketorolac will be prepared for IM injection by the nursing staff assigned to the patient once the following have taken place:

1. Study subject has granted consent
2. Pregnancy is excluded
3. Breast feeding is excluded
4. Inclusion criteria are met
5. None of the exclusion criteria are met
6. The ROS is complete
7. The attending provider agrees to the randomized dose and formally prescribes the randomized dose of ketorolac through the EHR
8. Ketorolac will then be prepared for IM injection by the nursing staff assigned to the patient

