##### 1. Objective adverse events

1. Objective adverse events will be described based on objective findings found during reassessment immediately following the initial ketorolac administration, and at the 30 minute and 60 minute re-evaluation intervals. Objective adverse events are any (1.) subjective events (signs or symptoms) which can be validated or observed by study investigators (such as rash or obvious dyspnea), (2.) are obvious to the investigator, but perhaps not the patient (mild facial swelling or rash) or (3.) abnormal vital signs. Blood pressure and heart rate measurements will be taken at the 30 minute and 60 minute intervals. Any deviation of blood pressure or heart rate which would meet exclusion criteria for this study would prompt immediate notification of the attending provider and the patient would be excluded from the study.

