**10.14 Managing Data (Data Management and/or Sharing Plan) and/or Human Biological Specimens for this Study:**

Include in this section the plan for acquiring data (both electronic and hard copy), access during the study, data/specimen storage and length of time stored, shipment/transmission, and the plan for storage and final disposition at the conclusion of the study. Describe any data agreements in place for accessing data within and/or outside of your institution (e.g., Data Sharing Agreement, Data Use Agreement, Business Agreements, etc.)

As outlined in the procedures section, data acquired will initially be obtained by the investigator via T-system™ home screen during the pre-screening process. Data collection will occur from the time the subject provides informed consent through the conclusion of the data collection period. As the primary outcome, subjective pain level will be obtained upon administration of intramuscular ketorolac then 30 and 60 minutes after administration. As the secondary outcome, adverse effects will be assessed for at 30 and 60 minutes after administration of intramuscular ketorolac. Descriptive statistics will also be obtained on the Ketorolac Research Form after informed consent is obtained.

The subjective pain levels will be annotated on the three VAS forms. The descriptive data and adverse effects will be annotated on the WBAMC Ketorolac Research Form. These forms will be placed within the document envelopes for the duration of the study. At the end of each study day, the data from each

study subject will be transcribed on to the Excel document on the PIs government issued laptop. The laptop will physically be in the PIs possession for the duration of the study.

The only human biological specimen which will be obtained will be urine. It will be used for a POC UHCG test in order to assess for pregnancy. These specimens will be obtained, handled, processed, and destroyed in accordance with WBAMC ED and hospital policies. The results of the POC UHCG will be reported verbally to the attending and/or via the T-System comments section in EHR, which does not require access to the subject's individual EHR for their specific ED encounter.

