There are other categories on the screen for vital signs and orders, but these do not display specific vital signs or specific orders, unless accessed by the user through “clicking” on these categories. The vital signs category will be accessed to determine if the patient’s heart rate, temperature and blood pressure meet inclusion criteria. However, for the purposes of this study-no other protected health information (PHI) or personally identifiable information (PII) will be accessed, viewed or used. Again, the T-System™ home screen will be used only to determine the age of the potential subject, their ESI category and their chief complaint (and vital signs, but this is during the screening process). This data will be used to prescreen and identify any potential subjects for this study and to initiate the recruitment process. The data identified during this process is not recorded anywhere. Patients meeting the three above prescreening criteria will be considered potential subjects.

When prescreening T-System™ for a chief complaint of MSK pain, it should be known that MSK pain is a blanket term which encompasses many different types of injuries and/or pain. For completeness, a definition of MSK pain, as pertinent to this study, is located in the definitions section of this document. However, for brevity, the term MSK pain will be utilized throughout the remainder of this document.

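### Adverse effects are scored only after the injection with no recorded baseline, so symptoms already present can count as events, inflating both rates and diluting the dose difference

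*Protocol*

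**What the plan says.** **What is scored.** Under Secondary Outcome Variable Data (Protocol 10.2), subjects are given a list of common adverse events: "Subjects will be advised to circle any of the adverse events that they are experiencing". The scoring rule follows: "Each circled adverse event will count as 1 in a binary numbering system". The description of the Ketorolac Research Form in 10.1 repeats this. It speaks of events due to ketorolac but gives no way of establishing that cause.

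**When it is scored.** Protocol 10.14 states that "adverse effects will be assessed for at 30 and 60 minutes after administration of intramuscular ketorolac". For objective events, 10.2 refers to "objective findings found during reassessment immediately following the initial ketorolac administration, and at the 30 minute and 60 minute re-evaluation intervals". Abnormal vital signs are one kind of objective event, and "Blood pressure and heart rate measurements will be taken at the 30 minute and 60 minute intervals". No pre-dose assessment of adverse effects is described.

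**What is known before the dose.** A review of systems is carried out with each patient before the injection. Of its content, the Medication Administration part of 10.1 says: "However, this information will not be documented on any forms and will not be accessed through the EHR". Vital signs are looked up at pre-screening (13.3): "The vital signs category will be accessed to determine if the patient’s heart rate, temperature and blood pressure meet inclusion criteria". The same section says of the pre-screening data: "The data identified during this process is not recorded anywhere". The listed contents of the Research Form include eligibility criteria but no pre-dose symptom or vital-sign values. The pre-treatment VAS is the one outcome for which a baseline is recorded.

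**How it is tested.** Protocol 11.6 plans a one-sided z-test of two proportions at 0.05 to show fewer adverse effects on the lower dose. The SAP plans a Fisher's exact test and does not state its sidedness.

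**The concern.** A subject who already feels nauseated or has a headache on arrival, and still feels so at 30 minutes, is told to circle that item, and it scores as an adverse event. Patients in the emergency department with acute neck, back or limb pain could plausibly have such symptoms before any drug.

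These symptoms do not depend on dose, and randomisation balances them on average. They therefore add about equally to both arms. Two things follow. The incidence reported for each dose is too high. The difference between the doses is also smaller than the true one, so the comparison has less chance of detecting a real dose effect.

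This matters because the expected benefit of the lower dose, set out in sections 9.6 and 14.4, rests partly on fewer adverse outcomes. A finding of no difference could reflect background symptoms rather than equal tolerability.

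**Working it through.** **Step 1. The plan's own figure.** Section 11.5 gives a margin of 13 mm, SD 27 mm, true difference 0 and one-sided alpha 0.05. With 55 per arm the noncentrality is 13 / (27 × √(2/55)) = 2.52 on 108 degrees of freedom, which gives power of 80.6%. The stated 80% reproduces. It concerns the VAS only; the documents state no power, sample size or assumed rate for adverse events.

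**Step 2. What the scoring rule counts.** Three provisions might keep pre-existing symptoms out:

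- *Eligibility.* Section 12.6 does not list headache, nausea, dizziness or drowsiness as exclusions, although section 14.1 names all four as ketorolac effects. Section 14.2 (item 4) would exclude patients with any further medical problem found in the history or review of systems, but this is not in the 12.6 list and has no threshold.
- *Vital-sign limits.* Systolic pressure below 90 or above 180 mmHg, or pulse below 50 or above 150 beats/min, bars entry. A post-dose value beyond these limits is probably new, and that patient is then excluded from the study. Within the limits, the documents do not say what counts as abnormal, and 14.1 lists hypertension among the effects. A pressure that was already raised could therefore be scored.
- *Investigator review.* Section 10.2 has the investigators agree on and categorise subjective events, but no stated step removes those already present.

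Any listed symptom that passes screening and persists is therefore counted under the rule as written.

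**Step 3. Effect on the comparison.** Let b be the share of subjects, equal in both arms, with at least one listed symptom before injection. Let q be the true rate of at least one new event, independent of b. Then:

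- observed rate = 1 − (1−b)(1−q) = b + (1−b)q
- observed difference = (1−b)(q60 − q15)

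**Step 4. Illustration.** Assumed, not from the documents: q15 = 12%, q60 = 30%. With 55 per arm, exact enumeration of the two binomials gives:

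| b | Observed 15 mg | Observed 60 mg | Difference (points) | Power, one-sided pooled z | Power, two-sided Fisher |
|---|---|---|---|---|---|
| 0 | 12.0% | 30.0% | 18.0 | 76% | 56% |
| 10% | 20.8% | 37.0% | 16.2 | 60% | 39% |
| 20% | 29.6% | 44.0% | 14.4 | 47% | 28% |
| 40% | 47.2% | 58.0% | 10.8 | 31% | 14% |

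For b = 20%: 0.20 + 0.80 × 0.12 = 0.296 and 0.20 + 0.80 × 0.30 = 0.440, so the difference is 0.144 = 0.80 × 0.18.

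**Step 5. A second scenario.** With 61 per arm and assumed rates of 10% and 30%, going from b = 0 to b = 20% lowers power from 88% to 58% (one-sided z, normal approximation) and from 74% to 38% (two-sided Fisher, exact). The pattern does not hang on one choice of rates.

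**The case against.** The best defence is that the protocol means to record only events caused by ketorolac, and that it screens patients before they are dosed. Every subject has a review of systems, section 14.2 excludes people with other medical problems, and eligibility is documented on the Research Form. These steps could keep b small. There is also an objective reassessment straight after the injection, which gives an early reference point. The percentages in section 14.1 are rates in treated patients, so they say nothing about how common these symptoms are before dosing. The outcome is secondary and carries no power claim. Under the assumed rates, two-sided Fisher power is only 56% even with b = 0.

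Most of this stands, and it limits the size of the problem. It does not remove it. The intention to attribute events has no recorded baseline behind it, and the post-injection check is not a baseline. A later judgement that a symptom was already present would rest on memory. It could also be made by someone who knows the arm, because the Subject Study Number shows the dose and appears on every form.

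A reader might infer two stronger things. One is that background symptoms would hide any dose difference. They do not: the difference shrinks by (1−b). The other is that blood pressure or heart rate already abnormal at triage necessarily counts as an effect of the injection. The entry limits rule out the extreme values, and abnormal is undefined within them, so the text supports only that such values could count.

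**Conclusion.** The concern holds as one of dilution and overstated rates. As written, the scoring rule can count symptoms present before the injection, and possibly vital signs that were already abnormal within the entry limits. The pre-dose information that would separate them is obtained but not recorded.

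That the incidence is overstated in both arms if any such subject enrols follows directly from the rule. The loss of power depends on b: under the illustration, 76% to 60% at b = 10% and 47% at b = 20% for the protocol's z-test. It rests on three assumptions: rates of 12% and 30%, the same b in both arms, and independence of background and drug-related symptoms. The documents give neither b nor rates by dose, so these figures show scale and are not estimates.

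The point affects the secondary outcome only. The VAS analysis and its 55 per arm are untouched. It should be corrected, because the baseline cannot be recovered once the subject has been dosed.

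**What to change.** - **Form.** Add a pre-dose column to the adverse-event checklist on the Ketorolac Research Form. The subject completes it together with the pre-treatment VAS, while the drug is being prepared.
- **Vital signs.** Record pre-dose blood pressure and heart rate on the same form, and state in the protocol what counts as abnormal for scoring.
- **Definition.** In 10.1 (Research Form description), 10.2 (secondary outcome and objective adverse events) and the SAP, define an adverse event for analysis as a listed symptom or abnormal vital sign that was absent before the injection or is worse after it.
- **Analysis.** Compare the proportion of subjects with at least one such event, and say so in both documents.
- **Consistency.** Amend the statements in 10.1 and 13.3 that pre-dose findings are not documented, so that they allow these entries.

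The cost is one column and one vital-sign entry on an existing form, about a minute per subject, and a few sentences of text. Event counts will be lower, because pre-existing symptoms no longer contribute.

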1. Ketorolac Research Form: this form documents age, gender, pain location, inclusion criteria, exclusion criteria, objective adverse effects, and subjective adverse effects. No PHI or PII will be annotated on this form.
  1. Age will be documented in years only. The actual date of birth will not be documented.
  2. Gender will be documented as "M" for male or "F" for female. Or an appropriate box will be "checked" by the potential subject indicating subject gender.
  3. Pain location will be free text, but will be qualified and isolated to an anatomical region. This will be at the discretion of the investigator. For instance, "heel pain" would be annotated as foot pain, or "calf pain" as leg pain. The anatomical regions designated for the purposes of this research are: (1.) neck pain, (2.) shoulder pain, (3.) arm pain, (4.) elbow pain, (5.) forearm pain, (6.) wrist pain, (7.) hand pain, (8.) hip pain, (9.) thigh pain, (10.) knee pain, (11.) leg pain, (12.) ankle pain, (13.) foot pain or (14.) back pain.
  4. See inclusion and exclusion section in this document for a detailed description of both.
  5. Adverse events which occur due to administration of intramuscular ketorolac will be documented as objective and subjective adverse effects. [Note, "adverse events" is a phrase used to describe adverse events, reactions, and effects to intramuscular ketorolac.] Subjects will be provided a list of known adverse events occurring in greater than 1% of patients during the U.S. Food and Drug Administration (FDA) trials, according to the medical website UpToDate.com. The list of adverse events will be included on the Ketorolac Research Form. Subjects will be advised to circle any of the adverse events that they are experiencing. Each circled adverse event will count as 1 in a binary numbering system (1 indicating an adverse event and 0 indicating no adverse event) for purposes of analysis. Subjects may have more than one adverse event and each event will count as 1 point. The definitions of objective and subjective adverse event are provided below.

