All appropriate provider and nursing policies, safeguards and regulations governing the preparation and administration of parenteral medication within the WBAMC ED will be followed and standard of care for the injection of ketorolac will not be altered, omitted or deviated from industry, ethical, moral or hospital standards. The investigators will not have any part in preparation or administration of the ketorolac-this will be completely handled by WBAMC ED nursing staff and the order for the ketorolac will have already been approved and prescribed by the WBAMC attending ED provider through the EHR.

As the medication is prepared for administration, the investigator will educate the subject on the use of the VAS and annotate their pre-treatment pain score on the VAS form. For the purposes of this study, the VAS is a validated tool that will be used to objectively measure the subject's response to ketorolac.

The subject will then be injected intramuscularly with the dose of ketorolac randomized to the patient based on the Subject Study Number assigned to the randomized packet, which was assigned to that subject. Again, all appropriate provider and nursing policies, safeguards and regulations governing the preparation and administration of parenteral medication within the WBAMC ED will be followed and standard of care for the injection of ketorolac will not be altered, omitted or deviated from industry, ethical, moral or hospital standards.

Following the administration of ketorolac and at the 30 and 60 minute intervals, VAS scores will be recorded, the patient will be assessed for adverse effects (objective and subjective) and blood pressure and heart rate measurements will be taken. At the conclusion of the 60 minute period and documentation of the VAS and any adverse effects, the data collection phase will be considered complete. The subject will be notified that the study has concluded. The attending provider will then continue with evaluation, treatment, and disposition, as indicated.

As outlined during the consent process, additional analgesia will be available during the course of the study. The decision to provide additional analgesia will be made by the attending provider in consideration of the study subject's clinical scenario. Study subjects who receive additional analgesia will be unenrolled from the study at the time of administration of the additional analgesia.

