##### 2. Subjective adverse events

1. Subjective adverse events are any symptoms conveyed by the subject, but are not measureable, observable or verifiable by the investigator. To better facilitate analysis, a list of the most common subjective adverse events, according to UpToDate.com, will be provided to the study subject to choose from. Examples of subjective adverse events may include dizziness, light headedness or nausea (this is not an exhaustive list of subjective

adverse events). Study investigators will review, confer, agree upon and categorize the adverse events (based on the subjective report) prior to submitting them to the statistician for analysis.

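### The adverse-event prompt asks about symptoms present when the subject is asked, which is narrower than the occurrence endpoint it feeds, so brief subjective events can go uncounted

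*Protocol*

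**What the plan says.** Protocol 10.2 (Secondary Outcome Variable Data) sets the endpoint: "The secondary outcome variables will be the number of subjects experiencing adverse events (both objective and subjective"). The same paragraph says where the data come from: "This data will be provided by the subjects or observed, measured or verified by the investigators". For what the subject reports, the only prompt given is "Subjects will be advised to circle any of the adverse events that they are experiencing". The next sentence scores a circled event 1 and the absence of an event 0. Prompt and scoring also appear in Protocol 10.1, in the description of the Ketorolac Research Form.

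On timing, Protocol 10.14 states that "adverse effects will be assessed for at 30 and 60 minutes after administration of intramuscular ketorolac". Protocol 10.1 (Medication Administration) says that after the injection and at those two times "the patient will be assessed for adverse effects (objective and subjective"). For objective events Protocol 10.2 adds a further look, giving "reassessment immediately following the initial ketorolac administration, and at the 30 minute and 60 minute re-evaluation intervals".

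Two statements are wider than the prompt. Protocol 10.1 introduces the item with "Adverse events which occur due to administration of intramuscular ketorolac will be documented as objective and subjective adverse effects". Protocol 10.2 defines the subjective class: "Subjective adverse events are any symptoms conveyed by the subject, but are not measureable, observable or verifiable by the investigator".

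The test is a one-sided z-test of two proportions in Protocol 11.6 and Fisher's exact test in the SAP. Either one needs a single yes/no value per subject.

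**The concern.** The endpoint concerns whether an event happened between the injection and 60 minutes. The prompt, taken at its word, asks whether one is present now. These agree for a symptom that lasts to the next check and differ for one that has already gone. Take a subject with nausea from minute 8 to minute 22. An adverse event occurred, but at minute 30 the subject is not experiencing it, and a literal answer leaves it uncircled.

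Adverse events are the only secondary outcome with a planned test, and Protocol 9.6 and 14.4 rest the expected benefit of the lower dose on fewer of them. If brief events are lost in equal proportion in both arms, the risk difference shrinks and a real advantage of 15 mg is harder to show. The reported percentages would also be low in both arms. The analyst cannot repair this later, because an event never recorded cannot be recovered.

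**Working it through.** **Setting the passages side by side**

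1. *What qualifies.* Protocol 10.1 covers events that occur because of the drug, and the subjective class covers any symptom conveyed. Neither requires the symptom to be ongoing.
2. *What is asked.* The one stated prompt is in the present tense. No section adds a recall period such as since the injection or since the last check.
3. *What is scored.* The circle is the score, so an uncircled subjective event contributes 0.
4. *Who else could catch it.* Investigators may record what they observe, measure or verify. By definition the subjective class is none of these, so for nausea, dizziness or lightheadedness the subject's report is the only source. A visible event between checks could be recorded if witnessed, though no section requires observation between checks.

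The gap is thus confined mainly to subjective events that start and end between checks and are not volunteered.

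**Size**

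The plan has no figure to reproduce here: it states no adverse-event rate by arm, no event duration and no power for this comparison. The 55 per arm (61 enrolled) in Protocol 11.5 is for the VAS comparison and does not depend on this wording.

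If a share d of affected subjects is detected, equally in both arms, the observed proportions are d·p60 and d·p15. The risk ratio is unchanged and the risk difference becomes d·(p60 − p15).

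*Illustration A; every input except alpha and n is an assumption.* Onset is uniform within each 30-minute interval, duration is exponential with mean D minutes, each affected subject has one event, and resolved events are never reported. Then

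d = (D/30)·(1 − exp(−30/D)).

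Take true proportions of 35% (60 mg) and 15% (15 mg), n = 55 per arm, and the protocol's one-sided 0.05 z-test:

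power = Φ[(Δ − 1.645·√(2·p̄(1−p̄)/n)) / √((p60(1−p60) + p15(1−p15))/n)], where Δ is the risk difference and p̄ the mean of the two proportions.

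Full capture: Δ = 0.20, p̄ = 0.25, so (0.20 − 1.645 × 0.0826)/0.0803 = 0.799 and power is 79%.

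D = 30: d = 1 − e^(−1) = 0.632. Proportions are 0.221 and 0.095, Δ = 0.126, p̄ = 0.158, so (0.1264 − 1.645 × 0.0696)/0.0685 = 0.175 and power is 57%.

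| Mean duration (min) | Detected d | Missed | Power |
|---|---|---|---|
| 15 | 0.432 | 57% | 43% |
| 30 | 0.632 | 37% | 57% |
| 60 | 0.787 | 21% | 67% |
| 120 | 0.885 | 12% | 73% |

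*Relaxing one assumption.* With two independent events per affected subject, the missed share is (1 − d)². At D = 30 it is 0.368² = 14% and power is 72%. At D = 60 it is 0.213² = 5% and power is 76%.

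*Illustration B, also assumed.* With 30% versus 15%, 61 per arm and 0, 10, 20 or 30% of affected subjects missed, expected counts are 18.3 v 9.2, 16.5 v 8.2, 14.6 v 7.3 and 12.8 v 6.4. Power is 63%, 58%, 53% and 48%.

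The loss runs from nothing to large, and no figure in the documents places the trial within that range.

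**The case against.** The strongest reply is that no rule scores a resolved event 0. The prompt is a form-filling instruction in ordinary present tense, and the endpoint sentence uses the same verb. The surrounding text is broader: events that occur, any symptom conveyed, events observed by investigators, and, in Protocol 16.1, a log of expected adverse events. A subject who mentions at minute 30 that nausea came and went meets the definition and can be counted. The Ketorolac Research Form is not reproduced, so its printed wording may already be wider. The size rests entirely on assumed rates and durations.

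Much of this stands. It means the undercount is possible and not certain, and that no power figure can be attached to it. It does not close the gap. The wider definitions say what would qualify if reported; they do not tell the subject to report something that has passed. Investigator observation cannot supply events defined as unobservable, and the log has no elicitation rule of its own. If the definitions do mean any occurrence after the dose, that confirms that the prompt is narrower than what it is meant to capture. And if the same resolved symptom may be counted or left out depending on how the subject reads one verb, the endpoint is not fixed in advance.

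**Conclusion.** The point holds as a mismatch between prompt and endpoint: the count of subjects with adverse events can be too low and the arm difference attenuated. The size is unknown. It is near zero if most events persist to the next check or subjects volunteer resolved ones; it grows with the share of brief, unvolunteered subjective events. The primary outcome and sample size are not affected.

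A reader might infer three stronger things that the documents do not support:

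- *That the count is certainly too low.* No section tells subjects to leave a resolved event uncircled, and the wider definitions allow it to be counted.
- *That power for this comparison falls to a particular value, such as 43%.* That depends on assumed rates, durations, one event per subject and no reporting of resolved symptoms.
- *That the comparison is biased between arms.* This would need event duration or reporting to differ by dose, and the documents give no information on that.

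This is a cheap improvement to a secondary outcome, worth making because unrecorded events cannot be recovered.

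**What to change.** In Protocol 10.1 (Ketorolac Research Form), Protocol 10.2 (Secondary Outcome Variable Data) and the form itself, replace the present-tense prompt. At 30 minutes ask for events experienced at any time since the injection; at 60 minutes, at any time since the last assessment. State that each subject scores 1 if any event occurred from injection to 60 minutes, and otherwise 0. This also gives the planned test of proportions its one yes/no value per subject, where the present text lets each event add a point.

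The change needs no extra visit, staff or procedure and alters nothing about treatment. Its downside is reliance on recall over at most 30 minutes.
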